## LIST OF ABBREVIATIONS

3D	3-dimensional
AE	Adverse Event
ALT	Alanine Aminotransferase
ANC	Absolute Neutrophil Count
ASCO-CAP	American Society of Clinical Oncology-College of American Pathologists
AST	Aspartate Aminotransferase
BUN	Blood Urea Nitrogen
C	Cycle
CBC	Complete Blood Count
CD	Cluster of differentiation
Cm	Centimeter
CMP	Comprehensive Metabolic Panel
CR	Complete Response
CT	Computed Tomography
CTCAE	Common Terminology Criteria for Adverse Events
CTL	Cytotoxic T-lymphocyte
CTLA	Cytotoxic T-lymphocyte-associated protein 4
CTV	Clinical target volume
D	Day
DNA	Deoxyribonucleic acid
DSMB	Data and Safety Monitoring Board
ECOG	Eastern Cooperative Oncology Group
ER	Estrogen Receptor
FDA	Food and Drug Administration
FISH	Fluorescence in-situ hybridization
FOXP3	Forkhead box P3
FSH	Follicle stimulating hormone
Gy	Gray
H&P	History & Physical Exam
HBsAg	Hepatitis B surface antigen
HCV	Hepatitis C virus
HER2	Human Epidermal Growth Receptor 2
HIV	Human immunodeficiency virus
HRT	Hormone replacement therapy
IB	Investigator's brochure
IDFS	Invasive Disease-Free Survival
IFN	Interferon
IHC	Immunohistochemistry
IL-2	Interleukin-2
IMRT	Intensity-modulated radiation therapy
irAE	Immune-related adverse event
IV	Intravenously

Kg	Kilogram
MerFISH	Multiplexed error-robust FISH
Mg	Milligram
miIHC	Multispectral immunohistochemistry
MK	Merck
MMG	Mammogram
Mo.	Month(s)
MRI	Magnetic resonance imaging
MTD	Maximum Tolerated Dose
N	Nodal status
NCI	National Cancer Institute
ORR	Objective Response Rate
PBMCs	Peripheral Blood Mononuclear Cells
PD	Progressive Disease
PD-L1	Programmed Death-Ligand 1
PFS	Progression Free Survival
PK	Pharmacokinetic
PR	Progesterone Receptor
PTV	Planning target volume
Q	Every
RNA	Ribonucleic acid
RT	Radiation Therapy
SAE	Serious Adverse Event
SBRT	Stereotactic body radiation therapy
SCOEPS	Safety Committee on Early Phase Studies
SD	Stable Disease
SEER	Surveillance, epidemiology, and end results program
SGOT	Serum Glutamic Oxaloacetic Transaminase
SOC	Standard of care
SPGT	Serum Glutamic Pyruvic Transaminase
SUSAR	Suspected Unexpected Serious Adverse Reaction
T	Tumor size
TCR	T-Cell Receptor
TIL	Tumor infiltrating lymphocyte
TNBC	Triple-Negative Breast Cancer
TNF- $\alpha$	Tumor necrosis factor-alpha
ULN	Upper limit of normal
US	Ultrasound
W	Week
WBC	White Blood Cells
WBRT	Whole breast radiation therapy
WOCBP	Women of child-bearing potential
YR	Year

[figure not shown]
## STUDY SCHEMA

This is a prospective, phase Ib/II study of the preoperative combination of pembrolizumab (pembro) and radiation therapy (RT) in patients with operable breast cancer. Patients with newly diagnosed, Stage I-III breast cancer who are planned for breast-conserving surgery and adjuvant whole breast radiation therapy will be recruited into one of 2 cohorts as per their biomarker profile as depicted below. The TNBC cohort will have 50 subjects (10 TNBC subjects for phase Ib and 40 TNBC subjects for phase II) and the HR+ cohort will have 10 subjects. Enrollment will start with the phase Ib TNBC cohort. The trial will be conducted in a Bayesian design, wherein safety as assessed by lack of delay in standard of care treatment will be assessed after 3, 6, and 9 patients have initiated standard of care treatment in each cohort. Standard of care treatment is defined as breast-conserving surgery or initiation of neoadjuvant systemic chemotherapy. If the phase Ib TNBC trial meets a pre-specified safety endpoint, enrollment in

the phase II TNBC trial and HR+ cohort will take place.

Study treatment will consist of 2 doses of neoadjuvant pembro. The second dose will be given in combination with a RT boost. The primary objectives are: 1) to assess the feasibility of the preoperative combination of pembro and RT as defined by the number of patients who do not necessitate a delay in standard of care treatment, 2) to assess the change in tumor infiltrating lymphocyte (TIL) score with therapy. The secondary objectives are to describe the toxicity with preoperative pembro and RT up to 15 weeks after administration of pembrolizumab, to assess the invasive disease-free (iDFS) survival, and to assess the pathological complete response (pCR) rates.

- The first dose of pembro will be given on cycle 1, day 1 (C1D1). Each cycle will be 21 days. The second of pembro dose will be given on C2D1 (+/- 3 days).
- RT will be administered concurrently within one week of the second dose of pembro (C2D1 + 5 calendar days). 8Gy will be delivered in 3 fractions over 3 to 5 business days (for a total dose of 24Gy).
- Standard of care treatment, including breast-conserving surgery or additional neoadjuvant systemic therapy, will be pre-set to start 8 weeks after study enrollment (+/- 5 days).
- Research blood and stool will be obtained after consent up to C1D1. It will also be obtained on C2D1 (+/- 3 days) and at the time of initiation of standard of care treatment (+/- 5 days).
- Research tumor biopsy will be performed after consent up to C1D1 (in the HR+ cohort, a diagnostic biopsy accepted if sufficient archived tissue is available) and on C2D1 (+/- 3 days) prior to the initiation of radiation therapy. Biopsies will be processed for scSeq and tumor infiltrating

- lymphocytes (TIL) analysis.
- Research tissue will also be obtained prior to the initiation of standard of care treatment at week 7 (+/- 5 days). If standard of care treatment consists of surgery, surgical tissue will be used. If it consists of further neoadjuvant systemic therapy, another research biopsy will be conducted. Fresh tissue may also be procured at the time of surgery if the surgery occurs after completion of neoadjuvant systemic therapy. This will be determined at the discretion of the treating physician.

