#### **Standard of Care Therapy**

The decision to proceed to breast-conserving surgery versus neoadjuvant systemic therapy will be at the discretion of the treating physician. Patients who are planned for neoadjuvant systemic

therapy will initiate treatment after study treatment completion. Either after neoadjuvant systemic therapy if planned or after study treatment, all patients will proceed to breast-conserving surgery. After surgery, patients will undergo adjuvant systemic treatment consisting of chemotherapy and/or endocrine therapy, as per physician's choice.

Following breast-conserving surgery, whole breast RT (WBRT) will be delivered as per standard of care. Given the hypofractionated boost approach, a standard fractionation of 200 cGy x 25 fractions (5 days a week for 5 weeks) will be utilized. Patients will begin WBRT approximately 4-6 weeks postoperatively or following chemotherapy.

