#### **6.2.1 Prior to Cycle 2**

##### **Research tests including:**

- Blood (3 CPT tubes, 1 red-top tube, and 1 green-top tube) for immune response studies.
- Core needle biopsy of primary tumor with 2 cores obtained for immune response studies.
- Optional breast MRI

- Optional fecal sample for microbiome analysis

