**6.2.2 Prior to standard of care treatment or at the time of surgery if that is the planned standard of care treatment**

**Research tests including:**

- Blood (3 CPT tubes, 1 red-top tube, and 1 green-top tube) for immune response studies.
- Core needle biopsy of primary tumor with 2 cores obtained for immune response studies or surgical sample with wedge of tumor tissue and benign tissue obtained.
  - If subject receives neoadjuvant systemic therapy before proceeding to surgery as part of SOC treatment, fresh specimen may also be collected at the time of surgery. This will be determined at the discretion of the treating investigator.
- Optional breast MRI
- Optional fecal sample for microbiome analysis
- **Cosmesis Evaluation (#2 if surgery is planned prior to SOC treatment)**

Cosmesis will be scored by the treating physician using the four-tier Harvard Scale (Excellent, Good, Fair, Poor) to compare the treated breast to the control breast.

- Digital photographs (frontal, with arms at side) will be recorded.

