## 8.2 Sample Collection / Specimen Banking

Research bloods to be used for flow cytometry analysis, measurement of circulating cytokines, and TCR sequencing will be collected prior to C1D1, on C2D1, and at the time

of initiation of standard of care treatment. Samples will be frozen and stored for subsequent analysis in the laboratory of [name].

Research biopsies will be conducted prior to C1D1 (standard of care diagnostic biopsy can be used if sufficient archived tissue available for the ER+ cohort), on C2D1, and at the time of initiation of standard of care treatment. If subsequent standard of care treatment is breast-conserving surgery, excision of tumor tissue+/- surrounding normal tissue can be collected in lieu of biopsy. At each time point, at least 2 cores (1cm each) will be collected. One will be frozen for flow cytometry analysis and MerFISH and the other will be paraffin embedded for TIL score, mIHC, and TCR and exome sequencing. For the ER+ cohort, if archived tissue is used in lieu of the first research biopsy, flow cytometry and MerFISH will not be conducted on this sample as fresh or frozen tissue is required for these studies.

If subjects receive neoadjuvant systemic therapy prior to proceeding to surgery as part of SOC treatment, fresh specimens may be collected at the time of surgery.

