**Table 9.2.3 Stopping rules based on seven interim looks**

Number of Patients	Number to Continue	Probability to Stop	Cumulative Probability to Stop
3	2	0.008	0.008
6	3	0.013	0.021
9	4	0.010	0.031
12	5	0.007	0.038
15	6	0.005	0.044
18	7	0.004	0.047
20	8	0.009	0.048

**Table 9.2.4 Design operating characteristics under different scenarios for the true probability of  $P_d$  for TNBC cohort**

True Value of $P_d$	Probability to Stop	Expected N	Expected N given that we Stopped
0.10	0.003	19.96	6.48
0.30	0.233	17.76	10.38
0.50	0.834	11.01	9.28
0.60	0.967	8.11	7.70

The co-primary efficacy endpoint will be change in TILs. TILs will be assessed in paraffin embedded samples after the study is completed and will have no bearing on impact on continued enrollment for the trial. For each cohort, the mean percent change in TIL score before treatment and after pembrolizumab alone  $\mu_1$  will be compared to the mean change in TIL score before treatment and after pembrolizumab plus radiation  $\mu_2$  using the paired t-test or Wilcoxon sign test depending on the distribution of the data. A significance of 0.05 will be used to declare statistical significance. Let  $SD(\text{diff})$  be the standard deviation of the difference in percent change in TIL score before treatment and after pembrolizumab and before and after treatment with pembrolizumab and radiation. Data from 8 evaluable patients in the HR+ cohort achieve 80% power to detect an effect size of 1.16 using a two-sided paired t-test at the 0.05 level of significance. The effect size is defined as the difference between the two means divided by  $SD(\text{diff})$ ,  $(\mu_1 - \mu_2) / SD(\text{diff})$ . This is equivalent to an absolute difference of 20% between the mean change in TIL scores assuming an  $SD(\text{diff})$  of 17%. For the TNBC cohort, assuming 16 patients are evaluable, the effect size that is detectable with the same power and type I error is 0.75.

Comparisons of clinical characteristics among cohorts will be conducted using descriptive summary statistics using median and range. Changes in TIL score will be compared between cohorts using Fishers exact test.

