5. All mononuclear cells (including lymphocytes and plasma cells) should be scored, but polymorphonuclear leukocytes are excluded.
6. One section (4–5 µm, magnification ×200–400) per patient is currently considered to be sufficient.
7. Full sections are preferred over biopsies whenever possible. Cores can be used in the pretherapeutic neoadjuvant setting; currently no validated methodology has been developed to score TILs after neoadjuvant treatment.
8. A full assessment of average TILs in the tumor area by the pathologist should be used. Do not focus on hotspots.
9. The working group's consensus is that TILs may provide more biological relevant information when scored as a continuous variable, since this will allow more accurate statistical analyses, which can later be categorized around different thresholds. However, in daily practice, most pathologists will rarely report for example 13.5% and will round up to the nearest 5%–10%, in this example thus 15%. Pathologist should report their scores in as much detail as the pathologist feels comfortable with.
10. TILs should be assessed as a continuous parameter. The percentage of stromal TILs is a semi quantitative parameter for this assessment, for example, 80% stromal TILs means that 80% of the stromal area shows a dense mononuclear infiltrate. For assessment of percentage values, the dissociated growth pattern of lymphocytes needs to be taken into account.

---

Lymphocytes typically do not form solid cellular aggregates; therefore, the designation ‘100% stromal TILs would still allow some empty tissue space between the individual lymphocytes.

11. No formal recommendation for a clinically relevant TIL threshold(s) can be given at this stage. The consensus was that a valid methodology is currently more important than issues of thresholds for clinical use, which will be determined once a solid methodology is in place. lymphocyte-predominant breast cancer can be used as a descriptive term for tumors that contain more lymphocytes than tumor cells. However, the thresholds vary between 50% and 60% stromal lymphocytes.

---

---

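### In surgery-route patients the TIL specimen changes from a needle core (Week 4) to excised tissue (Week 7), so the co-primary paired TIL difference can carry an unhandled specimen-type effect

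*Combined protocol and SAP*

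**What the plan says.** **Week 4.** Section 6.2.1 requires, before Cycle 2, "Core needle biopsy of primary tumor with 2 cores obtained for immune response studies". Section 8.2 adds that one core is frozen and the other is paraffin embedded for the TIL score and other assays. At the two-core minimum, the Week 4 TIL score rests on one core.

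**Week 7.** The Study Schema says "If standard of care treatment consists of surgery, surgical tissue will be used" and "If it consists of further neoadjuvant systemic therapy, another research biopsy will be conducted". Footnote 10 of the Time and Events Table repeats this split. Section 6.2.2 allows the biopsy "or surgical sample with wedge of tumor tissue and benign tissue obtained". Section 8.2 calls for at least two 1 cm cores at every time point, yet where surgery follows it says "excision of tumor tissue+/- surrounding normal tissue can be collected in lieu of biopsy".

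**Route.** Under Standard of Care Therapy: "The decision to proceed to breast-conserving surgery versus neoadjuvant systemic therapy will be at the discretion of the treating physician".

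**Analysis.** Section 9.2.1 compares, within each cohort, the change from baseline to after pembrolizumab with the change from baseline to after pembrolizumab plus RT, by paired t-test or Wilcoxon test. It then states "Changes in TIL score will be compared between cohorts using Fishers exact test". Section 2.4 says the serial assessment will establish what RT contributes. Section 9 has no stratification, matched-specimen rule or sensitivity analysis for specimen type.

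**Scoring guide.** Appendix B, item 7: "Full sections are preferred over biopsies whenever possible". The same item accepts cores in the pre-treatment neoadjuvant setting and says no validated method exists for scoring TILs after neoadjuvant treatment.

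**The concern.** A within-patient comparison is clean only if the measurement is made the same way both times. Here the specimen stays a core in chemotherapy-route patients and changes to excised tissue in surgery-route patients, at the very step the co-primary test examines. If excised tissue tends to score higher or lower than a core, that difference enters the paired result. Section 2.4 would then have it read as part of the RT contribution, or it would mask one. The problem remains even if the result is described only as Week 7 versus Week 4, because it concerns measurement rather than attribution.

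The route is chosen by the physician, so the share of patients affected is neither fixed nor known in advance. If the cohorts differ in route mix, the between-cohort comparison of TIL change would be affected as well.

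**Working it through.** **1. What the paired test reduces to.** Let B, W4 and W7 be the TIL scores at baseline, Week 4 and Week 7. On the absolute scale, (W7 − B) − (W4 − B) = W7 − W4, so baseline cancels. A specimen offset b enters in full for a surgery-route patient and not at all for a chemotherapy-route patient. If a share s goes to surgery, the bias in the mean is s × b; for example, 0.5 × 10 = 5 points.

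**2. The plan's own figures (Section 9.2.1).** Two-sided paired t-test, alpha 0.05, n − 1 degrees of freedom, noncentrality = effect size × √n.
- HR+, n=8, effect size 1.16: 1.16 × √8 = 3.28, power 80.3% (stated 80%).
- TNBC, n=16, effect size 0.75: 0.75 × 4 = 3.00, power 80.1% (stated 80%).
- The stated 20% difference over an SD of 17% is 20/17 = 1.18, power 81.3%, which agrees with 1.16 within rounding.

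The power statement is arithmetically right. It assumes that the paired difference contains only the treatment change.

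**3. Type I error with an offset and no true change.** From the plan: SD(diff) 17, n=8 and n=16. Assumed, because the documents give neither: an offset of 0 to 10 TIL points, and the share going to surgery. With all patients going to surgery the result is exact, with noncentrality (b/17) × √n; at n=8 this is 0.83 for b=5 and 1.66 for b=10. The other rows are simulated with normal differences. The range in the half-to-surgery rows runs from exactly half of the patients to each patient having a 50% chance.

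| n and share to surgery | offset 0 | offset 5 | offset 10 |
|---|---|---|---|
| 8, all | 5% | 11.2% | 30.2% |
| 8, half | 5% | 6.2–6.5% | 9.6–10.7% |
| 16, half | 5% | 8.2–8.5% | 17.4–18.5% |
| 16, 10% | 5% | 5.1% | 5.5% |

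For phase II TNBC, Section 9.2.1 says that surgery follows chemotherapy in most cases. The last row is therefore closer to that description than the third, although the text gives no percentage.

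**4. Power if the offset opposes a true 20-point difference, n=8.** With half going to surgery, power falls from 81% to about 70% (5 points) or 53–54% (10 points). With all going to surgery it falls to 57% or 30%.

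**5. Why an analysis-only repair is weak.** Keeping only core-to-core pairs after the fact removes the offset, but with half going to surgery it leaves n=4 in HR+, with 36% power at effect size 1.16.

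**6. Scale.** Section 9.2.1 speaks of percent change and Section 8.1 of fold-changes. On a relative scale the difference is (W7 − W4)/B, so an offset b becomes b/B and weighs more in low-TIL tumours. The figures above apply to the absolute TIL-point scale only.

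**The case against.** The strongest reply is that no document shows a systematic shift between cores and excised tissue. Appendix B already limits the obvious causes: it scores stromal percentage, only inside the invasive border, excludes necrosis and previous biopsy sites, and averages without seeking hotspots. A larger area then mainly improves precision. Its preference for full sections does not by itself establish a shift in the mean. This stands, and it is why the effect can only be called possible, with size and direction unknown. It does not show the offset to be zero, and the same guide says scoring after neoadjuvant treatment has no validated method.

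A second reply is that large error rates need extreme inputs. This also stands: 30% needs a 10-point offset and every patient going to surgery.

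Third, a reader might infer that specimen type is confounded with cohort. The documents do not support that as fact. The remark that most patients have chemotherapy first sits in the Phase II text, the TIL test sits under Phase Ib, and no route mix is given for HR+. Nor is a between-cohort error rate offered here: the plan names Fisher's exact test without saying how TIL change is categorised, and a figure from a t-test would not describe that test.

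Fourth, making post-treatment cores the only Week 7 score would go against the guide's preference for sections and could lose evaluable samples. The fix therefore keeps the section scored. Finally, TIL results do not affect enrolment, which limits the consequence to interpretation of the co-primary endpoint.

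**Conclusion.** The point holds as an uncontrolled source of bias, not a demonstrated one. Variation by route is explicit in the plan; variation by cohort is conditional on a route mix that the documents do not give. With an assumed offset of 0 to 10 points, SD(diff) 17 and the absolute scale, the nominal 5% error at n=8 becomes at most about 11% with half going to surgery, and up to 30% only if all do. At n=16 with a 10% surgery share it stays near 5-6%. A reader might conclude that the TIL result will show a false RT effect; the documents do not support that, since the offset could be near zero or could run against a true effect. The change is worth making because it is cheap and because a matched core not taken at surgery may not be recoverable later.

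**What to change.** - Reconcile the Study Schema, Section 6.2.2 and footnote 10 of the Time and Events Table with Section 8.2, which already calls for at least two 1 cm cores at each time point but lets excision replace biopsy. For surgery-route patients, state that cores of the same size are also taken from the excised tumour, and processed and scored like the Week 4 core.
- Use the matched core-to-core score for the Week 7 versus Week 4 paired test. Score the full surgical section alongside it as a labelled sensitivity analysis, and use the section where the core is not evaluable, with such cases identified.
- In Section 9.2.1, report the paired TIL difference by specimen type and route next to the pooled test.

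**Cost.** Minor pathology handling on tissue already removed, with no added patient procedure. A core samples less tissue than a section, so the Week 7 score will be somewhat noisier and some cores may not be evaluable.

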## STUDY SUMMARY

Title	Preoperative Combination of Pembrolizumab and Radiation Therapy in Patients with Operable Breast Cancer
Protocol Number	IIT2017-07-HO-PEMBRORT
Phase	Pilot Study; Phase Ib/II
Methodology	Prospective therapeutic trial
Study Duration	Approximately 5 years
Study Center(s)	Cedars-Sinai Medical Center
Objectives	
Primary Objectives:
 
 
• To assess the feasibility of the preoperative combination of pembro and RT as defined by the number of patients who do not necessitate a delay in standard of care treatment
 
• To assess the change in tumor infiltrating lymphocyte score with therapy
 
 
Secondary Objective:
 
 
• To describe the toxicity with preoperative pembrolizumab and RT up to 15 weeks after the last dose.
 
• To assess invasive disease-free survival (iDFS) rates.
 
• To assess the pathological complete response (pCR) rates
 

Number of Subjects	60
Diagnosis and Main Inclusion Criteria	Operable hormone receptor positive (HR+) or triple negative breast cancer (TNBC) with planned breast-conserving surgery and adjuvant whole breast radiation therapy
Study Product(s), Dose, Route, Regimen	Pembrolizumab 200mg IV every 3 weeks x 2 doses RT 8Gy x 3 fractions
Duration of administration	6 weeks
Reference therapy	None
Statistical Methodology	Bayesian design

---

